8. SAFETY ANALYSIS

8.1. General

Safety analyses will be performed on the safety analysis set. Summaries will be presented by treatment group in double-blind period for both the interim analysis at the end of the doubleblind period and for the interim analysis at the end of the open-label period (TEV-48125 225 mg monthly, TEV-48125 675 mg quarterly and placebo). A column for all fremanezumab-treated patients will be provided and a total column will also be provided.

For continuous variables, descriptive statistics (n, mean, SD, median, minimum, and maximum) will be provided for actual values and changes from baseline to each time point. For categorical variables, patient counts and percentages will be provided.

Missing values will be reported as missing and no imputation will be undertaken.

All data during the follow-up period, i.e., after the open-label period, will be listed only.

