2. STUDY OBJECTIVES AND ENDPOINTS

2.1. Primary and Secondary Study Objectives and Endpoints

Note that, for endpoints that are based on a monthly average, “baseline” refers to the monthly average value during the 28-day baseline period.

The primary endpoint was chosen based on the International Headache Society (IHS) guidelines for studies in migraine, which suggest that the most appropriate primary endpoint to capture efficacy of treatment is the change from baseline in the monthly average number of migraine days ([Silberstein et al 2008](#)).

The primary and secondary study objectives and endpoints are the following:

| Objectives | Endpoints |
|---|---|
| 
The primary objective of the study is to demonstrate the efficacy of fremanezumab administered as monthly and quarterly subcutaneous (sc) injections to adult Chinese patients with migraine. The primary efficacy analysis will consider all fremanezumab-treated patients as 1 group.
 | 
The primary endpoint is the mean change from baseline in the monthly average number of migraine days during the 12-week period after the 1st dose of investigational medicinal product (IMP).
 |
| 
The secondary objective of the study is to further demonstrate the efficacy of fremanezumab administered as monthly and quarterly sc injections to adult Chinese patients with migraine. The secondary efficacy analyses will consider all fremanezumab-treated patients as 1 group.
 | 
The secondary endpoints are as follows:
 
 • mean change from baseline in the number of migraine days during the 4-week period after the 1st dose of IMP • mean change from baseline in the monthly average number of days that any acute headache medications were used during the 12-week period after the 1st dose of IMP • proportion of patients reaching at least 50% reduction in the monthly average number of migraine days during the 12-week period after the 1st dose of IMP • mean change from baseline in the monthly average number of days with headache of at least moderate severity during the 12-week period after the 1st dose of IMP |
| 
A secondary objective of the study is to evaluate the safety and tolerability of fremanezumab administered as monthly and quarterly sc injections to adult Chinese patients with migraine.
 | 
The safety/tolerability endpoints are as follows:
 
 • occurrence of adverse events throughout the study |

| Objectives | Endpoints |

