7.1.2. Recording and Reporting of Adverse Events

For the recording of adverse events, the study period is defined for each patient as the time period from signature of the ICF to the end of the follow-up period. The follow-up period of the recording of adverse events is defined as 3 months after the last dose of IMP. The period for reporting treatment-emergent adverse events is defined as the period after the 1st dose of IMP is administered and until the end of the follow-up period.

All adverse events that occur during the defined study period must be recorded both on the source documents and the CRF, regardless of the severity of the event or judged relationship to the IMP. For serious adverse events, the serious adverse event form must be completed, and the serious adverse event must be reported immediately (Section 7.1.5.3.1). The investigator does not need to actively monitor patients for adverse events after the defined period. Serious adverse events and adverse events of special interest (Section 7.1.6) occurring after the defined study period should be reported to the sponsor if the investigator becomes aware of them, following the procedures described in Section 7.1.5.3.1.

At each contact with the patient, the investigator or designee must question the patient about adverse events by asking an open-ended question such as “Have you had any unusual symptoms or medical problems since the last visit? If yes, please describe.” All reported or observed signs and symptoms will be recorded individually, except when considered manifestations of a medical condition or disease state. A precise diagnosis will be recorded whenever possible. When such a diagnosis is made, all related signs, symptoms, and any test findings will be recorded collectively as a single diagnosis on the CRF and, if it is a serious adverse event, on the serious adverse event form.

The clinical course of each adverse event will be monitored at suitable intervals until resolved, stabilized, or returned to baseline; or until the patient is referred for continued care to a health care professional.

The onset and end dates, duration (in case of an adverse event, duration of less than 24 hours), action taken regarding the IMP, treatment administered, and outcome for each adverse event must be recorded both on the source documents and the CRF.

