9.7. Safety Analysis

Safety analyses will be performed on the safety analysis set.

Safety assessments and time points are provided in Table 3.

All adverse events will be coded using the Medical Dictionary for Regulatory Activities. Each patient will be counted only once in each preferred term or system organ class category for the analyses of safety. Summaries will be presented for all adverse events (overall and by severity),

adverse events determined by the investigator to be related to the test IMP (ie, reasonable possibility; defined as related or with missing relationship [overall and by severity]), serious adverse events, and adverse events leading to discontinuation from the study. Summaries will be presented by treatment group. Patient listings of serious adverse events and adverse events leading to discontinuation will be presented.

Changes in clinical laboratory, ECG, and vital signs measurements data will be summarized descriptively. All values will be compared with predefined criteria to identify potentially clinically significant values or changes, and such values will be listed.

The use of concomitant medications will be summarized by therapeutic class using descriptive statistics. Concomitant medications will include all medications taken while the patient is treated with the IMP.

Safety data will be summarized descriptively by treatment group. For continuous variables, descriptive statistics (n, mean, SD, median, minimum, and maximum) will be provided for actual values and changes from baseline to each time point. For categorical variables, patient counts and percentages will be provided. Descriptive summaries of serious adverse events, patient discontinuations due to adverse events, and potentially clinically significant abnormal values (clinical laboratory or vital signs) based on predefined criteria will be provided as well.

If any patient dies during the study, a listing of deaths will be provided, and all relevant information will be discussed in the patient narrative included in the CSR.

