2.5.2. Final Analyses and Reporting

All analyses identified in this SAP will be performed after the first interim database lock (at the end of the double-blind period) and after the second interim database lock (at the end of the open-label period) of this study. A final safety analysis will take place after the end of study as defined in the study protocol.

This SAP and any corresponding amendments will be approved before database lock, in accordance to GSD-SOP-702 (Statistical Analysis Plan).

The randomization codes will not be unblinded until this SAP has been approved and issued.

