4. GENERAL ISSUES FOR DATA ANALYSIS

4.1. General

Descriptive statistics for continuous variables include n, mean, standard deviation (SD), standard error (SE), median, minimum, and maximum. Descriptive statistics for categorical variables include patient counts and percentages; missing categories will be displayed as appropriate.

Data collected at the follow-up visit (visit 9) will be listed only.

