8.3. Adverse Events

All adverse events will be coded using the Medical Dictionary for Regulatory Activities (MedDRA) version 26.0 or higher.

For adverse event recording, the study period is defined for each patient as the time period from signature of the informed consent form to the end of the follow-up period. Adverse events will be presented separately for the double-blind period and for the open-label period.

Adverse events will be collected at each visit via adverse event inquiry.

The following are considered protocol-defined adverse events of special interest to be sent to the sponsor's Global Patient Safety and Pharmacovigilance for evaluation: severe hypersensitivity and anaphylaxis, as well as ophthalmic events of at least moderate severity.

Summaries will be presented by migraine classification for all treatment-emergent adverse events (overall and by severity), adverse events determined by the investigator to be treatmentrelated adverse events (ie, reasonable possibility; defined as related or with missing relationship [overall and by severity]), serious adverse events, protocol-defined adverse events of special interest, adverse events leading to discontinuation from treatment, adverse events leading to discontinuation from the study, non-serious adverse events, injection site reaction adverse events, adverse events requiring concomitant or additional treatment, and adverse events leading to death.

The incidence of adverse events will be summarized using descriptive statistics by migraine classification, PT and SOC. Each patient will be counted only once in each PT or SOC category for the analyses of safety. For the summaries by severity, patients are counted at the greatest severity. Adverse events with the missing flag indicating serious will be excluded from the summary of serious adverse events but included in the summary of non-serious adverse events.

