14. CHANGES TO ANALYSES SPECIFIED IN THE STUDY PROTOCOL

The following endpoint has been removed in the SAP due to the necessary data not being collected:

• mean change from baseline in the monthly average number of days with most bothersome symptoms during the 12-week period after the 1st dose of IMP

The wording of the following endpoint has been changed as shown.

Wording from protocol:

• mean change from baseline (day 0) of patient satisfaction, as measured by the PGIC scale, at 4 weeks after the last (6th) dose of study drug

New wording in SAP:

• assessment of patient satisfaction, as measured by the Patient Global Impression of Change (PGIC) scale, at visit 8

A multiple imputation analysis has been added in Section 6.2.3.2 as an additional sensitivity analysis of the primary estimand to assess the sensitivity of the primary analysis to missing data assuming the data is missing not at random.

The definitions for CM and EM have been modified; CM is defined as having ≥ 15 headache days during the baseline period whilst < 15 headache days during the baseline period is classed as EM.

The following analysis has been removed in the SAP due to minimal COVID-19 diagnoses occurring:

• Missing data or visits due to the COVID-19 pandemic will be evaluated for the primary and secondary endpoints. COVID-19 may have an impact on patients' migraine symptoms, with headache reported to be a common complication as a result of contracting the disease. All COVID-19 cases will be included in the primary analysis; however, observations following COVID-19 diagnosis will be discarded from the calculation of the monthly average endpoint. The data handling strategy will be detailed in the statistical analysis plan.

The following subgroup analysis has been removed in the SAP due to disease severity being collected daily rather than just once during the baseline period:

• Patients by disease severity (Mild, Moderate, Severe)

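### The SAP's adverse-event incidence tables stop at visit 8, leaving out the last 56 of the 224 days in the protocol's treatment-emergent window, and SAP 14 does not record the narrowing

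*SAP*

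**What the plan says.** **Protocol.** Section 7.1.2 sets the follow-up period for recording adverse events at 3 months after the last dose. On the reporting window it reads: "treatment-emergent adverse events is defined as the period after the 1st dose of IMP is administered and until the end of the follow-up period". Section 2.1 makes the first safety endpoint "occurrence of adverse events throughout the study", and SAP 1.1 repeats it unchanged. Section 9.7 states "Summaries will be presented for all adverse events (overall and by severity", and so on through related, serious and discontinuation events, with no cut-off at visit 8.

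**SAP.** Section 8.1 restricts what is tabulated: "All data during the follow-up period, i.e., after the open-label period, will be listed only". Section 4.1 has a matching rule: "Data collected at the follow-up visit (visit 9) will be listed only". Section 8.3 keeps the recording period open to the end of follow-up and asks for summaries of all treatment-emergent adverse events, without defining that term. It also says "Adverse events will be presented separately for the double-blind period and for the open-label period". Section 2.5.2 ties the SAP's analyses to the two interim locks and then adds "A final safety analysis will take place after the end of study as defined in the study protocol", without naming any output. Section 14, headed "CHANGES TO ANALYSES SPECIFIED IN THE STUDY PROTOCOL", lists items as small as the rewording of one patient-reported endpoint, but nothing about the adverse-event window.

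**The concern.** The SAP has two instructions that cannot both be followed. A programmer who takes treatment-emergent in its only defined sense would count events up to visit 9. A programmer who follows 8.1 would stop at visit 8. Section 8.1 is the more specific text and would probably win, so the incidence tables would cover a shorter period than the endpoint they report on.

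The endpoint is one of occurrence. A listing gives no incidence by preferred term, severity, seriousness or special interest, so a reader who wanted those figures over the protocol's own window would have to build them by hand. The study is unblinded at the first interim analysis (SAP 2.5.1). If the content of the final safety analysis is left open, it will be settled after that point.

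**Working it through.** **Inputs**

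- Visit 7 (last dose) day 141, visit 8 day 169 ±5, visit 9 day 225 ±15: protocol Table 3.
- Follow-up period, nominal days 169 to 224: SAP 4.4.
- Treatment-emergent window, first dose to the end of follow-up: protocol 7.1.2.
- Planned completers 328, planned randomized 372: protocol 3.2.

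**Reproducing the plan's own timing.** Table 3 puts visit 9 about 3 months after the last dose and 2 months after visit 8. With 28-day months:

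- Visit 9 − visit 7 = 225 − 141 = 84 days; 84/28 = 3.0 months.
- Visit 9 − visit 8 = 225 − 169 = 56 days; 56/28 = 2.0 months.

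Both agree with the plan.

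**Time left out of the tables, for a patient who completes on schedule**

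- Treatment-emergent window: days 1 to 224 = 224 days.
- Tabulated (double-blind plus open-label): days 1 to 168 = 168 days.
- Listed only: 224 − 169 + 1 = 56 days.
- Share of the window: 56/224 = 0.25.
- After the last dose: days 141 to 224 = 84 days, of which days 141 to 168 (28 days) are tabulated. Share listed only: 56/84 = 0.67.
- With the ordinary visit windows, visit 8 to visit 9 spans from (225 − 15) − (169 + 5) = 36 days to (225 + 15) − (169 − 5) = 76 days.

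**Scale across the trial.** If all 328 planned completers are followed for 56 days, the listed-only time is 328 × 56/365.25 ≈ 50 patient-years. If all 372 randomized patients are followed, it is 372 × 56/365.25 ≈ 57 patient-years.

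**Does any other SAP text put follow-up events in a table?**

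- SAP 8.1 ties safety summaries to the two interim analyses.
- SAP 8.3 names two periods and no whole-study table.
- SAP 2.5.2 promises a final safety analysis without content. Read with 4.1 and 8.1, its follow-up part can only be listings.
- The one text pointing the other way is the request in 8.3 for all treatment-emergent events. Without a definition in the SAP, it conflicts with 8.1 but does not override it.

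**The case against.** The best defence has four parts.

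**The SAP may do this.** Protocol section 9 sends changes to the SAP. Protocol 9.12 lets deviations be described in amendments, the SAP, the CSR or a combination. The SAP Introduction says that the SAP prevails and that the CSR will explain differences. The listing rule is stated openly, twice. This stands: a reader might infer a prohibited or hidden change, and the documents do not support that. What remains is a missing entry in SAP 14 and a conflict inside the SAP, which its precedence over the protocol does not settle.

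**Protocol 7.1.2 concerns recording and reporting, and 9.7 sets no window.** This is fair as far as it goes. But 7.1.2 holds the only definition of a term that SAP 8.3 uses to specify its tables, and the endpoint, repeated in the SAP, is not limited to treatment periods.

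**Little information is at risk.** SAP 8.3 lists events with onset day, severity and relationship, and SAP 8.4 gives deaths a listing and a narrative. SAP 9 counts patients who fail to complete the study because of adverse events. The open-label period runs to visit 8, so the first four weeks after the last dose are tabulated. All of this stands, and it rules out the reading that follow-up events are lost or unreported.

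**Follow-up data are uncontrolled and sparse.** There is no concurrent placebo group and, after visit 8, one scheduled contact. That is a good reason to show the data separately and descriptively. It could also justify listings alone, but the SAP does not make that argument.

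**Conclusion.** The point holds as an unrecorded narrowing and an internal inconsistency. The SAP's incidence tables omit nominal days 169 to 224, which is 25% of the protocol's treatment-emergent window and 67% of the time after the last dose. It should be corrected, but it is modest: no data are lost, and efficacy, sample size and type 1 error are untouched.

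A reader might infer that a quarter of adverse events drop out of the tables. The documents do not support that. The figures are shares of time, no follow-up event rate is given, and the tables count each patient once per preferred term or system organ class, so repeat events would not add to incidence. Nor do the documents give drug levels during follow-up, so the point does not rest on any stated amount of residual exposure.

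The shares assume a patient who completes on schedule. For patients who stop treatment early, the SAP does not say to which period their later events belong.

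**What to change.** Amend SAP 4.1, 8.1 and 8.3 to adopt the treatment-emergent definition in protocol 7.1.2. State in SAP 2.5.2 that the final safety analysis includes descriptive incidence tables of treatment-emergent, serious and special-interest adverse events through visit 9. Show these apart from the double-blind comparison, because follow-up has no concurrent placebo group.

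If the narrower window is intended, record it in SAP 14 with the reason, and give SAP 8.3 its own treatment-emergent definition so that it no longer conflicts with 8.1.

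The cost is a little extra table programming on data already collected. No visits, procedures or efficacy analyses change.

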8.2. Duration of Exposure to Study Drug

Duration of treatment (days treated) for the double-blind treatment period is the number of days on treatment starting from the 1^{st} study drug administration day to the week 12 or double-blind early withdrawal visit day (week 12 or double-blind early withdrawal visit day – first day of study drug + 1). For patients who are lost to follow-up during the double-blind treatment period, the EOT visit date is defined as the last study drug administration + 27.

Duration of treatment (days treated) for the open-label treatment period is the number of days on treatment starting from the 1^{st} study drug administration day in the open-label treatment period to the week 24 or open-label early withdrawal visit day (week 24 or open-label early withdrawal visit day – first day of study drug in the open-label treatment period + 1). For patients who are lost to follow-up during the open-label treatment period, the EOT visit date is defined as the last study drug administration + 27.

Duration of treatment (days) during the double-blind and open-label periods will be summarized using descriptive statistics.

8.3. Adverse Events

All adverse events will be coded using the Medical Dictionary for Regulatory Activities (MedDRA) version 26.0 or higher.

For adverse event recording, the study period is defined for each patient as the time period from signature of the informed consent form to the end of the follow-up period. Adverse events will be presented separately for the double-blind period and for the open-label period.

Adverse events will be collected at each visit via adverse event inquiry.

The following are considered protocol-defined adverse events of special interest to be sent to the sponsor's Global Patient Safety and Pharmacovigilance for evaluation: severe hypersensitivity and anaphylaxis, as well as ophthalmic events of at least moderate severity.

Summaries will be presented by migraine classification for all treatment-emergent adverse events (overall and by severity), adverse events determined by the investigator to be treatmentrelated adverse events (ie, reasonable possibility; defined as related or with missing relationship [overall and by severity]), serious adverse events, protocol-defined adverse events of special interest, adverse events leading to discontinuation from treatment, adverse events leading to discontinuation from the study, non-serious adverse events, injection site reaction adverse events, adverse events requiring concomitant or additional treatment, and adverse events leading to death.

The incidence of adverse events will be summarized using descriptive statistics by migraine classification, PT and SOC. Each patient will be counted only once in each PT or SOC category for the analyses of safety. For the summaries by severity, patients are counted at the greatest severity. Adverse events with the missing flag indicating serious will be excluded from the summary of serious adverse events but included in the summary of non-serious adverse events.

Listings for adverse events, deaths, serious adverse events, serious adverse events additional information, adverse events leading to discontinuation from treatment, adverse events leading to discontinuation from the study, injection site related adverse events requiring concomitant or additional treatment given, protocol-defined adverse events, protocol-defined adverse events of special interest, and adverse events for patients who did not meet screening criteria will be presented. All information pertaining to adverse events noted during the study will be listed by subject, detailing verbatim given by the investigator, PT, SOC, date of onset, date of resolution, severity, and relationship to treatment. The onset of adverse events will also be shown relative (in number of days) to the 1st day of treatment. In addition, MedDRA dictionary terms for adverse event descriptions, and adverse event preferred terms by patient number and treatment group will be presented.

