The relationship of each adverse event to the IMP and study procedures and the severity and seriousness of each adverse event, as judged by the investigator, must be recorded as described below.

Further details are given in the Safety Monitoring Plan.

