7.1.5.3. Reporting a Serious Adverse Event

7.1.5.3.1. Investigator Responsibility

To satisfy regulatory requirements, all serious adverse events that occur during the study, regardless of judged relationship to administration of the IMP, must be reported to the sponsor by the investigator. The event must be reported within 24 hours of when the investigator learns about it. Completing the serious adverse event form and reporting the event must not be delayed, even if not all the information is available. The investigator does not need to actively monitor patients for adverse events once this study has ended.

Serious adverse events occurring to a patient after the last administration of IMP of that patient has ended should be reported to the sponsor if the investigator becomes aware of them.

The serious adverse event form should be sent to the local safety officer (LSO) or designee (a contract research organization [CRO] in a country without a sponsor LSO) (contact information is in the Clinical Study Personnel Contact Information section); the LSO will forward the report to the sponsor's GPSP.

The following information should be provided to record the event accurately and completely:

- study number
- investigator and investigational center identification
- patient number
- onset date and detailed description of adverse event
- investigator's assessment of the relationship of the adverse event to the IMP (no reasonable possibility, reasonable possibility)

Additional information includes:

- age and sex of patient
- date of 1st dose of IMP
- date and amount of last administered dose of IMP
- action taken
- outcome, if known
- severity
- explanation of assessment of relatedness
- concomitant medication (including doses, routes of administration, and regimens) and treatment of the event
- pertinent laboratory or other diagnostic test data
- medical history

- results of dechallenge/rechallenge, if known
- for an adverse event resulting in death
 - cause of death (whether or not the death was related to IMP)
 - autopsy findings (if available)

Each report of a serious adverse event will be reviewed and evaluated by the investigator and the sponsor to assess the nature of the event and the relationship of the event to the IMP, study procedures, and to underlying disease.

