If data are processed from other sources (eg, central laboratory, bioanalytical laboratory, central image center, electronic diary data, or electronic patient-reported outcome [ePRO] tablet), these data will be sent to the investigational center, where they will be retained but not transcribed to the CRF unless otherwise noted in the protocol. These data may also be sent electronically to the sponsor (or organization performing data management). All patient data must have supportive original source documents in the medical records, or equivalent, before they are transcribed to the CRF. Data may not be recorded directly in the CRF and considered as source data unless the sponsor provides written instructions specifying which data are permitted to be recorded directly to the CRF.

For patients who enter a study but do not meet entry criteria, at a minimum, data for screening failure reason, demography, and adverse events from the time of informed consent will be entered in the CRF.

Data Quality Control

Data Management is responsible for the accuracy, quality, completeness, and internal consistency of the data from this study. Oversight will be carried out as described in the sponsor’s standard operating procedures (SOPs) for clinical studies. Day-to-day data management tasks for this study are delegated to a contract organization, and these functions may be carried out as described in the SOPs for clinical studies at that organization. These SOPs will be reviewed by the sponsor before the start of data management activities.

Data will be verified by the study monitor using the data source and reviewed by Data Management using both automated logical checks and manual review. Data identified as erroneous or data that are missing will be referred to the investigational center for resolution through data queries. Any necessary changes will be made in the clinical database, and data review and validation procedures will be repeated as needed. Data from external sources will be compared with the information available in the CDMS and any discrepancies will be queried.

Applicable terms will be coded according to the coding conventions for this study.

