2.4. Sample Size and Power Considerations

Using study data from 2 completed Phase 3 US pivotal studies in migraine, it is estimated that 163 completers per treatment group (ie, combined fremanezumab groups and placebo group) will provide at least 90% power to detect the assumed treatment difference at a significance level of 0.05. Assuming a 12% discontinuation rate, approximately 372 patients will be randomized in this study (93 patients in each fremanezumab treatment group and 186 patients in the placebo group). The primary efficacy analysis will consider all fremanezumab-treated patients as 1 group.

To ensure adequate representation of patients with both migraine types (EM and CM), the enrollment minimum of either migraine type is 30%. In addition, primary efficacy analysis will be stratified by EM and CM, and subgroup analysis for EM and CM will be conducted.

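### SAP 8.3 counts adverse events with a missing seriousness flag as non-serious, so any error from the rule is an undercount of serious events

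*SAP*

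**What the plan says.** SAP 8.3 sets an explicit rule for events with a blank seriousness flag: "Adverse events with the missing flag indicating serious will be excluded from the summary of serious adverse events but included in the summary" of non-serious events. In the same section, treatment-related events are "reasonable possibility; defined as related or with missing relationship", so a blank relationship is counted as related. Protocol 9.7 has the same rule for relationship ("reasonable possibility; defined as related or with missing relationship [overall and by severity") but no rule for missing seriousness. The general rule for safety data in SAP 8.1 is: "Missing values will be reported as missing and no imputation will be undertaken".

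The protocol does not expect blank flags. Section 7.1.2 says that "the severity and seriousness of each adverse event, as judged by the investigator, must be recorded as described below". Appendix H says: "Data identified as erroneous or data that are missing will be referred to the investigational center for resolution through data queries". For serious events, section 7.1.5.3.1 adds: "The event must be reported within 24 hours of when the investigator learns about it".

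**The concern.** An event that nobody has classified appears in the non-serious table as if an investigator had judged it non-serious. The SAP had two precedents of its own, the unfavourable value (as for relationship) or showing the value as missing (as in 8.1), and it used neither. It gives no reason and plans no sensitivity count.

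At stake is the accuracy of the serious adverse event table. The protocol's account of earlier studies (section 1.2.2.2) describes serious events as infrequent, so a single patient can be visible in a group's rate. The fields named in SAP 8.3 for the general adverse event listing do not include seriousness, so a reader may be unable to see there that a flag was blank.

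**Working it through.** The plan states no figure on this point, so there is none to reproduce. The check is a count.

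**Definitions, for one treatment group**
- s = patients with at least one event flagged serious
- m = further patients with no flagged serious event but at least one event with a blank flag
- t = those of the m with an unflagged event that is truly serious, so 0 ≤ t ≤ m

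**Patients counted as having a serious event**
- SAP 8.3 rule: s
- Truth: s + t
- Blank counted as serious: s + m

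Since s ≤ s + t ≤ s + m, the SAP count is never too high. It is exact when t = 0, that is, when no flag is blank or when every unflagged event is non-serious. Counting blanks as serious is never too low. Showing m in a separate row gives the reader both bounds.

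**Size per patient.** SAP 2.4 plans "93 patients in each fremanezumab treatment group and 186 patients in the placebo group". Assuming every planned patient is dosed:
- pooled fremanezumab (93 + 93 = 186) or placebo (186): 1/186 = 0.54 percentage points
- one regimen group: 1/93 = 1.08 points

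These are errors only for patients counted in t. For a patient in m but not in t, the SAP count is right.

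**Range.** The documents give no number of blank flags, so m is an assumption. The largest possible undercount in a group of 186 occurs when t = m:

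| assumed m | m/186 |
|---|---|
| 0 | 0 |
| 1 | 0.54 points |
| 2 | 1.08 points |
| 5 | 2.69 points |

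SAP 8.3 also presents adverse events by migraine classification, and SAP 2.4 lets either type fall to 30% of enrolment. At that floor, with balanced strata assumed, a group of 186 contributes 0.30 × 186 ≈ 56 patients and a group of 93 about 28. One patient is then 1/56 = 1.8 points or 1/28 = 3.6 points.

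**Between-group comparison.** The undercount applies to each group separately. The error in the fremanezumab-minus-placebo difference is −(t_F/n_F − t_P/n_P), where F and P denote the two groups and n the group size. It can have either sign.

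**The case against.** The best defence is that the two items need not share a rule. Protocol Table 5 calls an event related when a link to the drug cannot be excluded, so treating a blank relationship as related fits that definition. Seriousness requires a listed criterion to be met, and section 7.1.5.1 regards an event meeting none of them as non-serious. This makes non-serious an understandable default. It does not settle the matter, because that sentence concerns events assessed against the criteria and a blank flag records no assessment.

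The practical objection is stronger, and it stands. Seriousness must be recorded, missing data are queried, and serious events reach the sponsor within 24 hours on a separate form, independently of this table. An unflagged event also remains in the overall and by-severity summaries, and deaths are listed separately. Few blank flags, possibly none, should survive to lock.

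It is also fair to say that counting blanks as serious is itself imputation under SAP 8.1, and could put into the table an event that no investigator judged serious.

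Three stronger readings are tempting, and the documents support none of them:
- *Serious events will be understated.* The rule fixes the direction of any error. It does not show that an error will occur.
- *Flags will still be open at the first interim lock.* SAP 2.1 allows some safety fields to be updated after that lock, but its examples are stop date, outcome and action taken, not seriousness.
- *Safety oversight is weakened because there is no data monitoring committee.* Serious events are reviewed as they are reported (protocol 3.4), not through the SAP 8.3 summary.

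**Conclusion.** The point holds as a minor one. The rule assigns the favourable value to an unclassified event, against both the relationship rule beside it and the no-imputation rule in SAP 8.1, and any error it produces lowers the serious event count. The error is 0.54 points in the pooled or placebo group, or 1.08 points in one regimen group, per patient whose only serious event is unflagged and truly serious. These figures assume that all planned patients are dosed; how many patients are affected cannot be derived from the documents and may well be zero. The rule cannot be said to favour fremanezumab in the comparison with placebo. No efficacy result, type 1 error or sample size is affected.

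**What to change.** Amend SAP 8.3 as follows:

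1. Before each database lock, confirm by query and by reconciliation with the serious adverse event reports that no seriousness flag is blank.
2. Do not count a flag that is still missing as non-serious. Either count it as serious, stated as an exception to SAP 8.1 and matching the relationship rule, or show it in a separate row for missing seriousness, which is consistent with SAP 8.1.
3. Identify every such event in the adverse event listing.

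Possible wording for the first option: *An adverse event whose seriousness is still missing after query will be counted as serious, as an exception to Section 8.1, and identified in the listing.*

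The cost is a sentence or two in the SAP and a reconciliation check at each lock. If missing flags are counted as serious, the downside is a possible slight overstatement, which the listing makes visible. The separate row avoids that.
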